6.7.3. Prohibited Concomitant Therapy

The following concomitant medications are prohibited during the study:

Note: Subjects who enter the 4-Week Follow-Up Period will no longer need to abstain from the medications that were prohibited during the treatment periods, unless noted otherwise (eg, live attenuated vaccines for 4 weeks after the last dose of study drug). Once a subject has discontinued their study medication and had their Week 52 / ET visit, a subject may have their worsening Ulcerative Colitis / Ulcerative Colitis flare treated according to the local standard of care. The Investigator may initiate a rescue treatment during the Follow-Up period.

- Treatments for UC other than those listed in Section 6.7.2.1 (either approved or investigational)
- All live vaccines, during study treatment and within 4 weeks after the last administration of study treatment
- Moderate/strong inhibitors or inducers that inhibit or induce at least 2 of the following enzymes: CYP2C8, CYP2C9, and CYP3A4 (eg, fluconazole, rifampin, enzalutamide)

- Start, stop, or change in dosage of any anti-arrhythmic drugs (Class I to IV) within 1 week before or after treatment re-initiation following drug interruption as specified in Section 6.3.2.
- Chronic nonsteroidal anti-inflammatory drugs (NSAID) use (Note: Occasional use of NSAIDs and acetaminophen [eg, headache, arthritis, myalgias, or menstrual cramps] and aspirin up to 325 mg per day is permitted)
- Marketed biologic therapies
- Immunosuppressive agents (eg, AZA, 6-MP, tofacitinib)
- Any per rectum therapy including enemas (eg, 5-ASA, corticosteroid), other than that required for endoscopy preparation
- Cyclosporine, tacrolimus, sirolimus, methotrexate, or MMF
- Cholestyramine or other drugs interfering with enterohepatic circulation, unless the treatment has been stable for > 6 months prior to screening
- Any investigational drug other than the study treatment
- Treatment with D-penicillamine, thalidomide, dimethyl fumarate, or pyrimidine synthesis inhibitors
- Treatment with lymphocyte-trafficking inhibitors (eg, natalizumab, fingolimod, siponimod, ozanimod)
- Immunosuppressive agents that deplete lymphocytes (eg, alemtuzumab, anti-CD4, cladribine, rituximab, ocrelizumab, cyclophosphamide, mitoxantrone, daclizumab)

The following concomitant procedures are prohibited during the study:

- Major elective surgery
- Immunoadsorption columns
- IV immunoglobulin or plasmapheresis

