9.4.2. Treatment Period

After randomization, the 12-Week Treatment Period of the study will begin (Appendix 1, Table 6). A study visit window of \pm 3 days is permitted at each visit beginning with Week 2/Day 15 (PFT and OCT assessments have a window of \pm 7 days). After the Week 12 visit, a study visit window of \pm 7 days is permitted. Study visits should be scheduled for the morning.

The subscores for SF and RB are derived from the subject eDiary entries. On visits when MMS is calculated, these subscores are derived using the scores from the 3 most recent consecutive days within the 7 days prior to the day of bowel preparation (excluding the day of bowel preparation), averaged and rounded to the nearest integer. If 3 consecutive days are not available, then the average of the 2 most recent consecutive days within the 7 days will be used.

On visits without endoscopy, the SF and RB subscores are derived using the scores from the 3 most recent consecutive days within the 7 days prior to the date of visit, averaged and rounded to the nearest integer. If 3 consecutive days are not available, then the average of the 2 most recent consecutive days within the 7 days will be used.

It is recommended that procedures are performed in a consistent order and at approximately the same time of day for each visit. Below is the recommended sequence of events:

- Questionnaire administration
- Adverse event review
- Vital signs
- 12-lead ECG (as indicated in the Schedule of Assessments, Appendix 1, Table 6)
- Physical examination
- EIMs (as indicated in the Schedule of Assessments, Appendix 1, Table 6)
- PFT (as indicated in the Schedule of Assessments, Appendix 1, Table 6)
- OCT (as indicated in the Schedule of Assessments, Appendix 1, Table 6)
- Blood sample collection for laboratory tests and pre-dose PK sampling

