9.8.2.1. Endoscopy

A flexible proctosigmoidoscopy, performed with a video endoscope following cleansing preparation (oral or rectal cathartic), will be performed during screening (prior to Day 1/randomization), at Week 12, and at Week 52/ET visit. Additional proctosigmoidoscopies may be performed to confirm disease worsening and are required for qualification into the OLE (Section 5.1.1).

To ensure quality data and standardization, the same endoscopist should be used throughout the study wherever possible. Endoscopy images will be obtained during each endoscopy and will be sent for central reading and determination of the Mayo Clinic ES. A detailed image review charter from the central reading laboratory will outline the endoscopic procedures, video recordings, and equipment. For each subject, a video recording of the entire endoscopic procedure will be performed using an acceptable storage medium. The endoscopic recordings will be read centrally in a blinded manner for mucosal lesions and endoscopic severity by a qualified gastroenterologist according to the image review charter. The ES will be evaluated by the Investigator and the central reader. The central read will be used for determination of efficacy endpoints; however, treatment decisions will be made by the treating Investigator.

Repeated flexible proctosigmoidoscopy may be permitted by the Sponsor when the central reader indicates that the video endoscope data were acquired incorrectly or did not meet the minimal required quality standards.

Note: For subjects with pancolitis > 8 years duration or subjects with left-sided colitis > 12 years without a surveillance colonoscopy within 12 months prior to baseline (Section 4.1, Inclusion Criterion 6), a colonoscopy and biopsies taken in accordance with local standard of care at screening to rule out dysplasia (ie, in place of screening proctosigmoidoscopy) is required. Any adenomatous polyps must be removed prior to their first administration of study treatment.

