9.1.4. Definition and Use of Visit Windows in Reporting

All scheduled study visits are defined relative to Study Day 1, the date of first dose. Scheduled visit windows are defined in Clinical Study Protocol APD334-210 Amendment 2.0 Appendix 1: SCHEDULE OF ASSESSMENTS. A windowing convention will be used to determine the analysis visit value for a given measurement and will be applicable for all byvisit summaries and analyses for efficacy and safety data. Refer to Table 9 below for specific visit windows.

Table 9. Analysis Visit Windows for Efficacy and Safety Analyses

For all efficacy (except endoscopy/MI	MS/histology), efficacy-related biomarkers, safety labs and vital
signs	vis/instology), circucy related biomarkers, safety labs and vital
Scheduled Study Visit (Protocol	Analysis Visit Window (Study Day)
Scheduled Day)	
Baseline	≤1
Week 0 (Day 1)	1
Week 0 (Day 2) ^a	2
Week 2 (Day 15 ± 3)	2 to 22, or 3 to 22 ^a
Week 4 (Day 29 ± 3)	23 to 43
Week 8 (Day 57 ± 3)	44 to 71
Week 12 (Day 85 ± 7)	72 to 99
Week 16 (Day 113 ± 7)	100 to 141
Week 24 (Day 169 ± 7)	142 to 197
Week 32 (Day 225 \pm 7)	198 to 253
Week 40 (Day 281 ± 7)	254 to 309
Week 48 (Day 337 ± 7)	310 to 351
Week 52 (Day 365 ± 14)	> 351
	nposite endpoints that include an endoscopy component and/or
	Assessment, health-related quality of life, ECGs, OCT, and PFT
Scheduled Study Visit (Protocol	Analysis Visit Window (Study Day)
Scheduled Day)	
Baseline	≤1
Week 0 (Day 1)	1
Week 0 (Day 2) ^a	2
Week 12 (Day 85 ± 7) ^b	66 to 113 (66 to 141 for assessments impacted by COVID-19
	pandemic, or impacted by the war in Ukraine) ^c
Week 32 (Day 225 ± 7) [PFT only]	198 to 253 (198 to 281 for assessments impacted by COVID-19
	pandemic, or impacted by the war in Ukraine) ^c
	337 to 393 (337 to 421 for assessments impacted by COVID-19
Week 52 (Day 365 \pm 14) ^b	pandemic, or impacted by the war in Ukraine) ^c

a. Applicable only for participants who require extended monitoring on Day 2 for vital signs and ECGs.

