For cardiac remonitoring upon treatment reinitiation after Day 2, as manifested by more than 1 timed measurement in vital signs or electrocardiogram (ECG) parameters on the same collection date of an unscheduled visit, measurements will be mapped to analysis visit of Cardiac Remonitoring 1, Cardiac Remonitoring 2, etc. in the respective analysis dataset. For analysis, each timed measurement will be programmatically assigned to the nearest hourly timepoint (eg, Predose, 1-hour Postdose) based on their relationship to the dosing time on the same day. If the dosing date/time on the same day is missing, the timepoint will remain missing. Once mapped, these timed measurements from cardiac remonitoring visits will not be considered for any other analysis visit.

b Applicable to all Week 12 and Week 52 efficacy endpoints based on any component of Mayo clinic score, such as clinical remission and symptomatic remission.

c Assessments impacted by the COVID 19 pandemic are reported in the Date of Visit eCRF. COVID-19, coronavirus disease 2019; ECG, electrocardiogram; eCRF, electronic case report form; MMS, modified Mayo Score; OCT, optical coherence tomography; PFT, pulmonary function test; RB, rectal bleeding; SF, stool frequency. Assessments impacted by the war in Ukraine are reported in the protocol deviation document.

Windowing will be applied prior to any missing data calculations. The last nonmissing measurement taken prior to Day 1 (including unscheduled assessments) will be labeled as "Baseline". In the case where the last nonmissing measurement and the date of first dose coincide and time is not collected, if the measurement was planned in the protocol to be done prior to the date of first dose, that measurement will be labeled as "Baseline", not "Week 0". Unless stated otherwise, data from all visits including scheduled, unscheduled, and ET visits will be eligible for allocation to an analysis visit. The 2-Week and 4-Week Follow-Up visits will not be included in the visit windows and will be summarized separately without any window applied.

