If two or more measurements for an endpoint fall in a same analysis visit window, the measurement with the date closest to the protocol scheduled visit day will be used in the analysis. If 2 measurements in the same analysis visit window are equidistant from the protocol scheduled visit day, the earlier one will be used in the analysis. If multiple measurements are available on the same day, then the average of the measurements will be used in the analysis, except for laboratory and ECG data where the assessment at the earliest time of the same day will be used. If both central and local assessments of the same ECG or lab test are available on the same day, the central result will take precedence over the local result.

For the overlapping visit windows at Week 12 and Week 8/16, a hierarchical algorithm will be applied as follows: always map to the Week 12 study visit if the study day falls within the visit window of the Week 12 study visit, then assess the other records for the Week 8 or Week 16 study visit. The same algorithm will be used for Week 48 and Week 52, with Week 52 taking priority.

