9.3. Classification of Rescue Therapy

This appendix outlines the algorithm for the Pfizer clinical team/medical reviewers to classify rescue therapies for ulcerative colitis (UC) in a blinded manner. This will help establish intercurrent events for the efficacy estimands. All rescue therapies identified by the medical reviewers per the algorithm below will be imported in programming. This process will be repeated until database lock and the list of all rescue therapies identified will be finalized before study unblinding.

Only medications and medical procedures reported on the electronic case report forms (eCRFs) can be assessed whether they are rescue therapy for UC. If the exposure happens in the follow-up period (beginning on or after the date of last study treatment administration), then it would not be considered as a rescue therapy. Impact of rescue therapy use in the analysis is timing-dependent, eg, if a participant starts a rescue therapy between their Week 12 and Week 52 endpoint assessments, then it may have potential impact on Week 52 endpoint analysis but will have no impact on Week 12 endpoints. The rules outlined below apply to both new use and increase in dose from Baseline.

Biologics with immunomodulatory properties

- Rule:
 - Any exposure after first dose
- List of medications:
 - AntiTNFα antibodies:
 - ADALIMUMAB
 - CERTOLIZUMAB
 - CERTOLIZUMAB PEGOL
 - GOLIMUMAB
 - INFLIXIMAB
 - Other Biologics:
 - USTEKINUMAB
 - VEDOLIZUMAB
 - MIRIKIZUMAB

Nonbiologics with immunomodulatory properties

- Immunosuppressants
 - Rules to consider for Week 12 efficacy endpoints:
 - After first dose and up to and including Week 8: any increase from baseline for more than 5 days
 - After Week 8: Any dose above baseline
 - Rules to consider for Week 52 efficacy endpoints:
 - After Week 12 and up to and including Week 40: any increase from baseline for more than 5 days
 - After Week 40: Any dose above baseline
 - List of medications:
 - Thiopurines
 - MERCAPTOPURINE
 - o AZATHIOPRINE
 - TIOGUANINE
 - METHOTREXATE
 - METHOTREXATE SODIUM
- 5-ASA COMPOUNDS
 - Rules to consider for Week 12 efficacy endpoints:
 - After first dose and up to and including Week 8: any increase from baseline for more than 5 days
 - After Week 8: Any dose above baseline
 - Rules to consider for Week 52 efficacy endpoints:
 - After Week 12 and up to and including Week 40: any increase from baseline for more than 5 days
 - After Week 40: Any dose above baseline

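### SAP 9.3 ignores rescue begun on or after the last dose, even when the Week 52 endoscopy that is scored takes place later

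*SAP*

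**What the plan says.** **Rescue.** Estimand 1 (SAP 2.2.3) makes a participant a nonresponder for starting rescue medication, raising the dose of an existing UC medication, or having a rescue procedure. All three are identified through SAP 9.3. That section excludes exposure in follow-up, which it dates from the last dose: "beginning on or after the date of last study treatment administration), then it would not be considered as a rescue therapy". The next sentence uses a different anchor. It says that "if a participant starts a rescue therapy between their Week 12 and Week 52 endpoint assessments", the Week 52 analysis may be affected.

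**Week 52 window.** For endoscopy, MMS and histology, SAP Table 9 gives "337 to 393 (337 to 421 for assessments impacted by COVID-19" or by the war in Ukraine). SAP 9.1.4 adds that "data from all visits including scheduled, unscheduled, and ET visits will be eligible for allocation to an analysis visit"; only the 2-Week and 4-Week Follow-Up visits are left out. Where several measurements fall in one window, "the measurement with the date closest to the protocol scheduled visit day will be used in the analysis". The protocol's own visit tolerance is narrower: in Protocol 9.4.2, after Week 12, plus or minus "7 days is permitted".

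**Conduct.** Protocol 6.7.3 lets a flare be treated once study drug has stopped and the Week 52 or early termination visit is done: "The Investigator may initiate a rescue treatment during the Follow-Up period". Protocol 9.8.2.1 states: "Repeated flexible proctosigmoidoscopy may be permitted by the Sponsor when the central reader indicates" that the video was acquired incorrectly or fell below the quality standard.

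**The concern.** Two clocks are in use. Whether rescue counts is decided by the date of the last dose. Whether an endoscopy is scored is decided by its distance from Day 365. Nothing makes the first date at least as late as the second. When the last dose comes first, any rescue begun in the interval is ignored and the endoscopy after it is still scored.

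Early discontinuers are nonresponders through intercurrent event 1, so only participants who complete treatment are concerned. For them, a response achieved on rescue would be credited to the randomised arm. Endoscopic improvement at Week 52 is the first key secondary endpoint in the fixed testing sequence of SAP 5.1, and histologic-endoscopic mucosal improvement comes later in the same sequence.

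No other planned analysis would reveal it. The sensitivity analyses in SAP 5.3.1.2 vary only the handling of missing outcomes, and here the outcome is observed. The mPAS analysis in SAP 5.4 uses data as observed. SAP Table 2 removes the Per Protocol Set.

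**Working it through.** **1. The plan's own figures.** The documents give no count of affected participants. The only usable denominators are the planned arm sizes, 122 and 61 (Protocol 10.2, SAP 2.3). The power stated for them reproduces: Fisher's exact test at 34% versus 14% gives 83.8% (stated: at least 80%). The normal approximation gives 89.95% with unpooled variance, in effect the stated 90%; pooled variance gives 84.6%.

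**2. How long the gap can be.** Gap = last day of the analysis window minus day of last dose. The documents do not state the last-dose day. I assume that dosing ends at a Week 52 visit within the protocol tolerance, Day 358 to Day 372.

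| Last dose | Ordinary window (to Day 393) | COVID-19 or war (to Day 421) |
|---|---|---|
| Day 358 | 393 − 358 = 35 days | 421 − 358 = 63 days |
| Day 365 | 393 − 365 = 28 days | 421 − 365 = 56 days |
| Day 372 | 393 − 372 = 21 days | 421 − 372 = 49 days |

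These are maxima. The gap is zero whenever dosing continues to the endoscopy.

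**3. One case through the rules** (dates are illustrative). Last dose and Week 52 visit on Day 365; video unreadable; a listed rescue medication begun on Day 367; repeat endoscopy on Day 385 with ES 1.
- Intercurrent event 1: not met, because treatment was completed.
- Rescue: Day 367 is after Day 365, so SAP 9.3 excludes it.
- Window: Day 385 is before Day 393, so the score maps to Week 52.
- Closest-day rule: no help, because the unreadable video gave no score and the repeat is the only measurement.
- Result: responder for endoscopic improvement, and for histologic-endoscopic improvement if the biopsy qualifies.
- Clinical remission: also needs RB and SF from the 7 days before bowel preparation (SAP 3.1.1), here roughly Days 377 to 384. Protocol Table 6 schedules no diary review or SF/RB subscores at the follow-up visits. Without diary entries the participant is a nonresponder under SAP 5.3.1.1.

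**4. Other rules on timing.**
- The second sentence on timing in SAP 9.3 is tied to the endpoint assessments, not the last dose.
- The class rules in SAP 9.3 (any biologic exposure after the first dose; for most other classes, any dose above baseline after Week 40) have no last-dose limit.
- Protocol 10.4 makes those who start a disallowed agent nonresponders from then on, also without a last-dose limit.
- SAP Table 2, which lists departures from the protocol's analysis, does not mention the cut-off.

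**5. Effect per case.** Change in an arm's rate = 1/n.
- Etrasimod: 1/122 = 0.82 points, which raises the difference by 0.82.
- Placebo: 1/61 = 1.64 points, which lowers the difference by 1.64.
- Two etrasimod cases and one placebo case: 2/122 − 1/61 = 0, no net shift.

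**The case against.** The best defence is that the protocol already fixes the order. Protocol 6.7.3 allows rescue only after study drug has stopped and the Week 52 visit has taken place, and the endoscopy belongs to that visit. On protocol, rescue follows the assessment and should not count. Dosing normally runs up to the visit, and participants entering the extension stay on blinded drug until the day before its Day 1 (Protocol 5.1.1, 9.4.3), so their last dose normally follows the endoscopy. A valid on-time endoscopy also beats a later one under the closest-day rule.

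All of this stands, and it makes cases rare. It does not close the gap. After an unreadable video the Week 52 visit has occurred, so rescue followed by a permitted repeat endoscopy is no deviation. Where an endoscopy is delayed and rescue comes first, that may be a deviation, but no SAP rule turns it into nonresponse.

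A reader might infer that every endoscopy scored near Day 393 or 421 is contaminated. It is not: the last dose must precede it and rescue must begin in between. A reader might also infer that the primary endpoint and the symptom endpoints are exposed as much as endoscopy. The diary requirement argues against that. For 12-week corticosteroid-free remission, new steroid use before Week 52 is caught by the endpoint's own definition.

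**Conclusion.** The point holds as a gap and an internal inconsistency in SAP 9.3. For a completer whose scored Week 52 endoscopy follows the last dose, rescue begun in between is not counted, contrary to the intent of Estimand 1. The main exposure is endoscopic improvement and histologic-endoscopic mucosal improvement at Week 52. Clinical remission is at risk only if qualifying diary scores exist.

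The size is about 0.8 points per etrasimod case and 1.6 per placebo case, taking 122 and 61 as the analysed numbers. The interval is at most 21 to 35 days, or 49 to 63 under the COVID-19 or war extension, given the assumed last-dose range.

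Two further inferences are not supported. One is that the rule favours etrasimod: a placebo case shrinks the difference, and the documents say nothing on how many cases there are or in which arm. The other is that Week 12 needs the same change: the last-dose cut-off does not reach participants still on treatment, and SAP 9.3 already ties timing to the endpoint assessments. The correction is worth making because it is cheap and the rule is wrong as written, not because a large effect has been shown.

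**What to change.** In SAP 9.3, for Week 52 endpoints, replace the last-dose cut-off with: *Rescue begun after the last assessment contributing to the endpoint (endoscopy, biopsy or diary day) is not considered.* Listed rescue begun before that assessment, including after the last dose, then counts as the intercurrent event. Treatment started after the assessment stays excluded. Align the timing sentence and the class rules in 9.3 with this cut-off, and check it against Protocol 10.4. Leave the Week 12 rules unchanged.

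The cost is one SAP sentence and one date comparison in programming, within the blinded review that 9.3 already requires to be final before unblinding. Concomitant medications are recorded through the safety reporting period (Protocol 6.7). If that is the 30 days after the last dose in Protocol 9.9.9.2.2, it covers a gap of 28 days but not all of the longer ones, so for those few the medication record should be checked up to the endoscopy. The downside is that a very few responders may become nonresponders.
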